#### **4.9.2.2. Immune Response**

For viral load, cytokine, and protein data, descriptive summaries and analyses will be performed on logarithm base 10 transformed data and a value of 1 will be added to the original value before the transformation. Plasma concentration values that are below the limit of quantitation (BLQ) will be presented as “BLQ” in the concentration data listing. Values that are BLQ will be treated one-half the value of the lower limit of quantitation (LLOQ). The conventions are detailed in Section 6.3 .

#### **Reduction in cytokine levels, potentially including interleukin (IL)-2, IL-6, IL-7, IL-17, granulocyte-colony stimulating factor (GSF), interferon- $\gamma$ inducible protein 10, monocyte chemoattractant protein 1, macrophage inflammatory protein 1- $\alpha$ , and tumor necrosis factor- $\alpha$**

Descriptive statistics will be provided for each inflammatory cytokine such as IL-2, IL-6, IL-7, IL-17, GSF etc. at baseline, at each study visit post baseline for actual values and changes from baseline by treatment groups. Unless otherwise specified, only scheduled visits will be included in the summary tables. In the event of repeated values for a test at a visit, the last non-missing value at that visit will be used.

A by-subject listing will also be provided for cytokine data.

#### **Reduction in levels of acute phase proteins, potentially including ferritin, C-reactive protein, D-dimer, and cardiac troponin**

Descriptive statistics will be provided for each acute phase protein at baseline, at each study visit post baseline for actual values and changes from baseline by treatment groups. Unless otherwise specified, only scheduled visits will be included in the summary tables. In the event of repeated values for a test at a visit, the last non-missing value at that visit will be used.

A by-subject listing will also be provided for acute phase protein data.

#### **Normalization in the complete blood count**

Normalization of complete blood count is defined as all blood components such as WBC, RBC, HGB, HT, HCV, HCH, HCHC, and platelets return to the lab normal range post baseline during the study for subjects who had out of the normal range value of any of the blood component at baseline.

Number and percentage of subject achieving normalization of complete blood count in subjects with abnormal complete blood count at baseline will be summarized by treatment groups.

### **Changes in other laboratory parameters potentially including decreases in lactate dehydrogenase, prothrombin time, and albumin**

Descriptive statistics will be provided for each laboratory parameter at baseline, at each study visit post baseline for actual values and changes from baseline by treatment groups. Unless otherwise specified, only scheduled visits will be included in the summary tables. In the event of repeated values for a test at a visit, the last non-missing value at that visit will be used.

A by-subject listing will also be provided for laboratory data.

#### **4.9.2.3. Reduction in Viral Load**

Descriptive statistics will be provided for subjects' viral load at baseline, at each study visit post baseline for actual values and changes from baseline by treatment groups. Unless otherwise specified, only scheduled visits will be included in the summary tables. In the event of repeated values for a test at a visit, the last non-missing value at that visit will be used.

A by-subject listing will also be provided for the viral load data.

#### **4.9.2.4. Duration of Hospitalization**

Duration of hospitalization is defined as the sum of the days stayed in hospital. Descriptive statistics (such as mean, standard deviation, median, minimum, and maximum) of duration of hospitalization will be provided by treatment groups.

A by-subject listing will also be provided.

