2.2.2. Secondary Endpoints

Secondary endpoints of the study are as follows:

- The proportion of subjects requiring invasive ventilation at any point during the study
- The proportion of subjects requiring supplemental oxygen or non-invasive ventilation at any point during the study in subjects who did not require supplemental oxygen at baseline
- Time from randomization to defervescence in subjects presenting with fever at enrollment (temperature of ≥37.6°C axilla, ≥38.0°C oral, or ≥38.6°C tympanic or rectal)
- Time from randomization to respiratory rate ≤24 breaths/minute on room air
- Time from randomization to cough reported as mild or absent (on a scale of severe, moderate, mild, absent, in those with cough at enrollment rated severe or moderate)

- Time from randomization to dyspnea reported as mild or absent (on a scale of severe, moderate, mild, absent, in those with dyspnea at enrollment rated as severe or moderate)
- Attenuation of immune responses as indicated by:
 - reduction in cytokine levels, potentially including interleukin (IL)-2, IL-6, IL-7, IL-17, G-CSF, IP-10, MCP-1, MIP1- α , and TNF- α
 - reduction in levels of acute phase proteins, potentially including ferritin,
 C-reactive protein, D-dimer, and cardiac troponin
 - normalization in the complete blood count
 - changes in other laboratory parameters potentially including decreases in lactate dehydrogenase, prothrombin time, albumin
- Reduction in viral load
- Duration of hospitalization measured in days
- Mortality at Day 28
- Overall safety profile characterized by type, frequency, severity, timing, and relationship to study treatment of any adverse events (AEs) or laboratory abnormalities.

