3. STUDY DESIGN

3.1. Overall Design

This is a randomized, double-blind, placebo-controlled, multicenter 28-day study, with a safety follow-up telephone call at Day 60.

The study population is hospitalized adult subjects with confirmed pneumonia, diagnosed with COVID-19, and not requiring mechanical ventilation. For the purposes of enrollment of subjects into the study, "hospitalized patients" will include any COVID-19 patient either admitted or under observation in the hospital for a continuous period of 24 hours or more who otherwise fulfills the eligibility criteria.

Subjects will be randomized 1:1 to PTC299 treatment or placebo using a central randomization process, with approximately 190 subjects in each cohort. The randomization will be stratified by age (≤62 vs >62), remdesivir use (yes vs no), and dexamethasone use (yes vs no). All subjects will also receive standard of care (SOC), defined as the SOC per local written policies or guidelines. The use of steroids (except dexamethasone), sensitive CYP2D6 substrates, CYP2C inducers, IL-6 neutralizing antibodies, IL-6 receptor inhibitors, and any investigational therapies are prohibited.

Following eligibility screening and enrollment, subjects will receive oral tablets containing PTC299 or matching placebo 200 mg twice daily (BID) (morning and evening) on Days 1 to 7 and 50 mg once daily (QD) in the morning on Days 8 to 14.

Approximately 40 subjects (20 in each arm) will be enrolled initially, enrollment will then halt, and an interim analysis will be performed to assess safety. No formal statistical testing will be performed at the interim analysis. An independent data safety monitoring board (DSMB) and an independent HAC will review available data for the 40 subjects. Enrollment will continue if there are no safety concerns.

A second interim analysis is planned to assess futility. It will be performed when 50% of respiratory improvement events have been reached, ie, 163 events have been observed (approximately 190 subjects).

Subjects will be assessed daily while hospitalized. All subjects will undergo efficacy, safety, and laboratory assessments as summarized in Table 3. There will be a follow-up telephone call at Day 60 to assess AEs, SAEs, and deaths.

For subjects who are discharged from the hospital prior to Day 28:

- If SpO₂ is <94%, SpO₂ measurements will be taken daily until Day 28
- Subject-reported assessments for cough and dyspnea will continue to Day 28

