8.4.3. Analysis of Secondary Efficacy Endpoints

Similar to the primary endpoint, Kaplan-Meier estimate, median and rate at Days 7, 14, and 28 will be presented for time from randomization to defervescence (in subjects presenting with fever at enrollment), time from randomization to respiratory rate ≤24 breaths/minute on room air, time from randomization to cough reported as mild or absent (in those with cough at enrollment rated severe or moderate), and time from randomization to dyspnea reported as mild or absent (on a scale of severe, moderate, mild, absent, in those with dyspnea at enrollment rated as severe or moderate).

The proportion of subjects requiring invasive ventilation at any point during the study, subjects requiring supplemental oxygen or non-invasive ventilation at any point in the study in subjects without supplemental oxygen or non-invasive ventilation at baseline, subjects with normalization of the complete blood count, and the number of subjects who died at the end of the study will be summarized by frequency and percent.

The following secondary endpoints will be summarized descriptively

- Reduction in cytokine levels, potentially including IL-2, IL-6, IL-7, IL-17, G-CSF, IP-10, MCP1, MIP1-α, and TNF-α,
- Reduction in levels of acute phase proteins, potentially including ferritin and C-reactive protein, D-dimer, and cardiac troponin,
- Changes in other laboratory parameters including lactate dehydrogenase, prothrombin time, albumin,
- Reduction in viral load, and
- Duration of hospitalization measured in days

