#### **2.1.2. Secondary Objectives**

- To evaluate the clinical efficacy of PTC299 compared with placebo, as assessed by respiratory function, immune response, length of hospitalization, and mortality.
- To evaluate the safety of PTC299 as assessed by drug related adverse events.

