##### 4.9.1. Primary Efficacy Analysis

The primary endpoint is the time from randomization to respiratory improvement (T2RI), defined as  $\text{SpO}_2 \geq 94\%$  on room air sustained until discharge from the hospital or the end of the study (Day 28).

All hospitalized subjects will be followed fully to Day 28 with efficacy measurements taken daily unless they die, are lost to follow-up, or withdraw consent. For subjects who are discharged from the hospital prior to Day 28 without achieving respiratory improvement,  $\text{SpO}_2$  measurements will be taken daily until Day 28. All measurements recorded will be used for efficacy analysis.

Subjects who achieved  $\text{SpO}_2 \geq 94\%$  and sustained to Day 28 or discharge without taking any COVID-19 rescue therapy during the study will be considered as achieving respiratory improvement event and the event date will be the first date of achieving  $\text{SpO}_2 \geq 94\%$ . For all other subjects i.e., a). randomized but had no follow-up; b). initiated any COVID-19 rescue therapy during the study, where a rescue therapy is defined as any additional medication, exclusive of SOC, used to treat worsening of COVID-19 symptoms and recorded as rescue therapy on the eCRF; c). lost follow-up prior to Day 28 d). died prior to Day 28; e). withdrawn consent prior to Day 28; f). had full follow-up without achieving sustained  $\text{SpO}_2 \geq 94\%$ , will be censored at Day 28.

Kaplan-Meier (KM) plots of time to respiratory improvement will be presented. Median time to respiratory improvement will be estimated via the Kaplan-Meier product limit method.

A two-sided 95% confidence interval (CI) for the median time to respiratory improvement will be computed for PTC299 and placebo cohorts based on a log-log transformed CI for the survivor function  $S(t)$ . Time to respiratory improvement will be compared between treatment groups using stratified log-rank test by randomization strata.

Hazard ratio and corresponding two-sided 95% CIs will be estimated using a Cox proportional hazards model, with treatment arm as a single covariate, stratified by the stratification factors.

Respiratory improvement rates at Days 7, 14, and 28 will also be estimated using KM estimates on the time to respiratory improvement curve. Associated two-sided 95% CIs for each treatment group and the difference between the 2 treatment groups will be calculated using Greenwood's formula for variance derivation.

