**Time from randomization to respiratory rate  $\leq 24$  breaths/minute on room air**

Respiratory rate  $\leq 24$  breaths/minute on room air and sustained until discharge or Day 28 will be considered as achieving the respiratory rate normalization event. Time from randomization to the first date of achieving normalization of respiratory rate will be analyzed using KM method by treatment groups. A summary table of the number of events, the number of censors, and KM estimates (25th, 50th, 75th percentile of time to normalization of respiratory rate along with the 95% CI), and the rate of normalization of respiratory rate at Day 7, Day 14, and Day 28 will be provided.

Hazard ratio and corresponding two-sided 95% CIs will be estimated using a Cox proportional hazards model, with treatment arm as a single covariate, stratified by the stratification factors.

A KM plot by treatment groups will be provided for time from randomization to respiratory rate normalization and a by-subject listing will also be provided.

**Time from randomization to cough reported as mild or absent (on a scale of severe, moderate, mild, absent, in those with cough at enrollment rated as severe or moderate)**

Time from randomization to cough relief will only be analyzed in subjects with cough self-reported as severe or moderate at baseline on a scale of severe, moderate, mild, or absent. Cough relief event is defined as subjects with cough self-reported as severe or moderate at baseline and reported as mild or absent during the study and sustained until discharge or Day 28. Time from randomization to the first date of achieving cough relief event will be analyzed using KM method by treatment groups. A summary table of the number of events, the number of censors, and KM estimates (25th, 50th, 75th percentile of time to cough relief along with the 95% CI), and the cough relief rate at Day 7, Day 14, and Day 28 will be provided.

Hazard ratio and corresponding two-sided 95% CIs will be estimated using a Cox proportional hazards model, with treatment arm as a single covariate, stratified by the stratification factors.

A KM plot by treatment groups will be provided for time from randomization to cough relief and a by-subject listing will also be provided.

**Time from randomization to dyspnea reported as mild or absent (on a scale of severe, moderate, mild, absent, in those with dyspnea at enrollment rated as severe or moderate)**

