#### **4.10.2. Death**

The number and the percentage of deaths at Day 28 and Day 60, respectively, will be summarized by treatment groups.

All deaths will be presented in a by-subject listing.

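### Duration of hospitalization has no rule for in-hospital death or for a stay still open at Day 28, so an early death reads as a short stay (minor)

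*SAP*

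**What the plan says.** Length of hospitalization is one of the efficacy measures named in the secondary objective: the drug is compared with placebo "as assessed by respiratory function, immune response, length of hospitalization, and mortality" (SAP 2.1.2; protocol 2.1.2 agrees). The endpoint in protocol 2.2.2 is "Duration of hospitalization measured in days".

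The whole definition is in SAP 4.9.2.4: "Duration of hospitalization is defined as the sum of the days stayed in hospital". Mean, standard deviation, median and range follow by arm, with a by-subject listing. Protocol 8.4.3 puts the endpoint under the line "The following secondary endpoints will be summarized descriptively" and adds no counting rule. No test is planned.

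Death is handled elsewhere. For the primary endpoint, the list in SAP 4.9.1 of subjects censored at Day 28 includes those who "died prior to Day 28; e). withdrawn consent prior to Day 28"; protocol 8.4.2 has the same rule. SAP 4.10.2 adds: "The number and the percentage of deaths at Day 28 and Day 60, respectively, will be summarized by treatment groups". Neither rule is linked to length of stay.

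**The concern.** A short stay is meant to be a good outcome. As defined, a stay that ends in death and a stay that ends in recovery enter the mean and median on the same footing. The SAP avoids this for the primary endpoint by holding deaths to Day 28 without an event, but does not carry the idea over. An arm with more early deaths can therefore appear to leave hospital sooner.

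Two smaller gaps sit in the same sentence. Nothing says how a stay still open at Day 28 enters the sum. Nothing starts the count at randomization, although eligible patients are those "either admitted or under observation in the hospital for a continuous period of 24 hours or more" (protocol 3.1), so some hospital time can precede randomization. With randomized arms, that earlier time adds noise, not bias.

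At stake is how a reader interprets one of the efficacy measures in the secondary objective.

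**Working it through.** The documents give no expected stay, death rate or timing of death, so there is no plan figure to reproduce. Every input below is an assumption, varied to show the range.

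**Inputs.** Survivors' mean stay L = 12 days in both arms (10 and 15 also tried). Deaths occur on day d, the same in both arms unless stated. Mortality q is 5% vs 15%, or 6% vs 8%.

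**1. Mean as written.** Arm mean = L(1 − q) + d·q, so with common L and d the gap between arms is (difference in q) × (L − d). At d = 5:
- q = 5%: 12 × 0.95 + 5 × 0.05 = 11.65 days
- q = 15%: 12 × 0.85 + 5 × 0.15 = 10.95 days
- the arm with three times the deaths looks 0.70 days better

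| Death day | Mean, 5% mortality | Mean, 15% mortality | Gap, 15% minus 5% | Gap, 8% minus 6% |
|---|---|---|---|---|
| 5 | 11.65 | 10.95 | −0.70 | −0.14 |
| 7 | 11.75 | 11.25 | −0.50 | −0.10 |
| 12 | 12.00 | 12.00 | 0 | 0 |
| 18 | 12.30 | 12.90 | +0.60 | +0.12 |

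At 5% vs 15% and d = 5, L = 10 gives 0.10 × 5 = 0.50 days and L = 15 gives 0.10 × 10 = 1.00 day.

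**2. Timing alone.** With 10% mortality in both arms but deaths at Day 5 in one and Day 15 in the other, the means are 12 × 0.9 + 0.5 = 11.3 and 12 × 0.9 + 1.5 = 12.3 days. With equal mortality and equal timing the gap is zero.

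**3. Median as written against time to discharge alive.** Let survivors' stay be gamma (shape 2, scale 6, mean 12) with distribution function F, and deaths fall on Day 5.
- As written, (1 − q)F(t) + q = 0.5. At 5%, F = 0.45/0.95 = 0.474 and t = 9.6 days. At 15%, F = 0.35/0.85 = 0.412 and t = 8.5 days.
- Discharge alive, (1 − q)F(t) = 0.5. At 5%, F = 0.5/0.95 = 0.526 and t = 10.6 days. At 15%, F = 0.5/0.85 = 0.588 and t = 11.9 days.
- Discharged alive by Day 28, with F(28) = 0.947: 0.95 × 0.947 = 90% and 0.85 × 0.947 = 80%.

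The ranking of the arms reverses. It also reverses with shape 4 (10.6 vs 9.8 as written, 11.4 vs 12.3 discharge alive) and with exponential stays (7.7 vs 6.4, and 9.0 vs 10.7).

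**4. Open stays.** Under the shape 2 gamma, 1 − F(28) = 5.3% of survivors' stays run past Day 28. Capping them at 28 moves the mean from 12.0 to 11.6 days, so the unstated rule is worth about 0.4 days. It cancels between arms unless the share of long stays differs.

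**The case against.** The case for leaving this alone is fair. The summary is descriptive. Deaths are tabulated by arm at Day 28 and Day 60 and listed by subject, and so is length of stay. A contrast of 5% vs 15% would be about 9.5 vs 28.5 deaths in 190 per arm; with pooled mortality 10%, z = 0.10/√(0.10 × 0.90 × 2/190), about 3.2. Nobody who saw that mortality table would take a 0.7-day shorter stay as benefit. At the milder 6% vs 8% the shift is 0.14 days or less.

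Most of this stands, and it sets the severity. It does not close the gap, because separate tables of stay and of deaths do not show how much of a shorter stay is death. The reader would have to rebuild that from the listings.

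Two stronger readings are tempting. One is that the definition could produce a false efficacy claim or favours the drug. The documents do not support it: no test is attached, and the direction depends on which arm has more deaths and when.

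The other is that the respiratory-rate endpoint in SAP 4.9.2.1 is wrong because, unlike fever, cough and dyspnea, it is not limited to subjects abnormal at baseline: "Time from randomization to the first date of achieving normalization of respiratory rate will be analyzed using KM method by treatment groups". Inclusion criterion 7 does admit subjects on cough alone. But using everyone follows the ITT rule in SAP 4.2.1. The event also requires room air, and no section gives the share already meeting it. In simulation (380 subjects, exponential medians of 8 and 11 days borrowed from the primary endpoint, none worsening), the all-subject hazard ratio was 1.35 and 1.33 at shares of 5% and 10%, against about 1.38 in subjects able to improve. It fell to 1.26 and 1.16 only at shares of 25% and 50%. When 30% of baseline-normal subjects worsened on placebo and 20% on drug, the planned analysis did at least as well at every share: its interval excluded 1 in 81/79/74/67% of trials at 5/10/25/50%, against 80/78/70/52% in the restricted set. The baseline rule in SAP 6.1 is worded for safety parameters and plausibly covers respiratory rate already, since protocol 7.4 counts vital signs among the safety assessments. That leaves an optional supplement, not a fault.

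**Conclusion.** The omission is certain from the text; its impact is conditional. The definition lacks a rule for in-hospital death and for stays open at Day 28, and can rank the arms the wrong way if early deaths are unequal. Under the assumed 12-day survivors' mean and deaths at Day 5, the distortion in the mean is 0.70 days at 15% vs 5% mortality and 0.14 days at 8% vs 6%. It vanishes when mortality and timing match, or when deaths fall at the survivors' mean stay, and changes sign for later deaths. None of the inputs comes from the documents.

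The consequence is possible misreading of a descriptive secondary measure. Type I error, the primary analysis and the sample size are untouched. This is a minor point, worth settling because it is cheap.

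**What to change.** In SAP 4.9.2.4:
- Add time from randomization to first discharge alive, with death before discharge held as not discharged to Day 28 (the SAP 4.9.1 rule), summarised by Kaplan-Meier by arm. Holding deaths in this way makes the curve one minus the cumulative incidence of discharge alive, provided no one else is censored before Day 28.
- Keep the raw day counts as a descriptive table placed beside mortality, counted from randomization, with a stated rule for stays open at Day 28.
- List the addition in SAP Section 5, which now reports no change from the protocol, before database lock.

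Optional, and not a correction: beside the planned ITT respiratory-rate analysis, report by arm how many subjects are already at 24 breaths/minute or below on room air at baseline. If that share is material, show a supplementary analysis without them. Its limits are fewer subjects and no view of prevented worsening, which the ITT analysis keeps.

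The cost is slightly more analysis work. No new data should be needed, since a day count already requires the discharge or death date, and the existing time-to-event code can be reused.

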### **4.10. Safety Analysis**

All safety analyses will be performed on the safety population. Summary tables will be provided by treatment groups.

#### **4.10.1. Adverse Events**

All adverse events (AEs) will be coded using the MedDRA. The MedDRA version will be indicated in the footnote of relevant AE tables based on the current version used in the clinical data.

AEs will be analyzed in terms of treatment-emergent adverse events (TEAEs), which are defined as any AEs that occurring on or after the first study treatment through 30 days after the last dose, or any AEs occurring before the first study treatment but worsening during the treatment through 30 days after the last dose.

A treatment related TEAE is defined as TEAE that is suspected (possibly or probably related) by the investigator to be related to the study treatment. The severity/intensity of AEs will be graded 1 to 5 according to the National Cancer Institute (NCI) Common Terminology Criteria for Adverse Events (CTCAE) version 5.0. For AEs not described in CTCAE criteria, the intensity will be assessed by the investigator as mild (Grade 1), moderate (Grade 2), severe (Grade 3), life threatening (Grade 4), and fatal (Grade 5).

An overview of TEAE summary by treatment groups table will be provided with following information:

- The number of subjects with at least one TEAE
- The number of subjects with at least one treatment related TEAE
- The number of subjects with at least one Grade 3 or Grade 4 TEAE
- The number of subjects with a Grade 5 TEAE (Fatal)
- The number of subjects with at least one SAE

The number of subjects with at least one TEAE leading to treatment discontinuation.

All TEAEs will be summarized by MedDRA system organ class (SOC), and PT. If a subject experiences multiple AEs under the same SOC, the subject will be only counted once for the SOC with the greatest severity. Similarly, if a subject experiences multiple AEs under the same PT and SOC, the subject will be counted only once for the PT with the greatest severity.

The table will be sorted by the descending order of the frequency of SOC then by the descending order of the frequency of PT under SOC based on the PTC299 column.

In addition, the following summary tables will be provided:

- All TEAE by descending frequency of PT
- All TEAE by maximum severity under each SOC and PT
- SAE by SOC and PT
- Treatment related TEAE by SOC and PT
- TEAE leading to treatment discontinuation by SOC and PT

All TEAEs will be presented in a by-subject listing. Listings for non-treatment-emergent AEs, DLTs, SAEs, TEAEs leading to treatment discontinuation, TEAEs leading to dose reduction/interruption, and TEAEs leading to death will also be provided.

